APPENDIX A – REGISTRATION GUIDELINES AND FORMS

The following guidelines have been developed in order to ensure timely registration of your patient.

All patients entered on any CCCWFU trial, whether treatment, companion, or cancer control trial, **must** be registered with the CCCWFU Protocol Registrar or entered into ORIS Screening Log within 24 hours of Informed Consent. Patients **must** be registered prior to the initiation of treatment.

In order to ensure prompt registration of your patient, please:

1. Complete the Eligibility Checklist (attached)
2. Complete the Protocol Registration Form (attached)
3. Alert the WFUHS registrar by phone, *and then* send the signed Informed Consent Form, Eligibility Checklist and Protocol Registration Form to the registrar, either by fax or e-mail.

Contact Information:

Protocol Registrar [contact]

Protocol Registrar [contact]

Protocol Registrar E-MAIL ([contact])

*Protocol Registration is open from 8:30 AM - 4:00 PM, Monday-Friday.

4. Please fax/e-mail ALL eligibility source documents with registration. Patients **will not** be registered without all required supporting documents.

Note: If labs were performed at an outside institution, please provide a printout of the results. Please ensure that the most recent lab values are sent.

Comprehensive Cancer Center of Wake Forest University
A Pilot Study: Open-Label Clinical Trial of CPI-613 in Patients with Advanced Bile Duct
Cancers
CCCWFU # 59212

CCCWFU # 59212

Eligibility Checklist

Yes	No	N/A	Inclusion Criteria (All responses must be YES in order to enter study)	Eligibility Confirmation (registrar)
			1. Does the patient have histologically and cytologically proven cholangiocarcinoma of any type (including intrahepatic cholangiocarcinoma, extrahepatic primary cholangiocarcinoma, hilar cholangiocarcinomas, cholangiocarcinomas located in the gall bladder or hepatic capsule effraction, and carcinoma of the Ampulla of Vater, etc.) that is not amenable to surgery, radiation, or combined modality therapy with curative intent, and has failed or is not eligible for available chemotherapies such as gemcitabine with or without platinum?	
			2. Does the patient have local, locally-advanced, or metastatic disease documented as having shown progression on a scan (e.g., CT, MRI)?	
			3. Does the patient have measurable tumor according to RECIST 1.1 criteria with at least one unidimensionally measurable target lesion?	
			4. Does the patient have no evidence of biliary duct obstruction, unless obstruction is controlled by local treatment or, in whom the biliary tree can be decompressed by endoscopic or percutaneous stenting with subsequent reduction in bilirubin to below 1.5x Upper Level of Normal (ULN)?	
			5. Is the patient free from acute toxic effects from previous treatment superior to grade 1 at the start of the study?	
			6. Does the patient have an ECOG performance status of 0 to 2?	
			7. Is the patient's expected survival greater than 3 months?	
			8. Is the patient a male or female age 18 years and older?	
			9. If the patient is a woman of child-bearing potential (i.e., premenopausal or not surgically sterile), does she agree to use accepted contraceptive methods (abstinence, intrauterine device [IUD], oral contraceptive or double barrier device) during the study, and agree to have a negative serum or urine pregnancy test within 1 week prior to treatment initiation?	
			10. If the patient is a fertile man, does he agree to practice effective contraceptive methods during the study, unless documentation of infertility exists?	

Comprehensive Cancer Center of Wake Forest University
A Pilot Study: Open-Label Clinical Trial of CPI-613 in Patients with Advanced Bile Duct
Cancers
CCCWFU # 59212

CCCWFU # 59212

Eligibility Checklist

			
11. Does the patient have documentation (≤ 2 weeks) of the following laboratory values?:
 
 • Adequate hematologic (granulocyte count $\geq 1500/\text{mm}^3$; white blood cell [WBC] ≥ 3500 cells/mm^3 or ≥ 3.5 bil/L; platelet count $\geq 100,000$ cells/mm^3 or ≥ 100 bil/L; absolute neutrophil count [ANC] ≥ 1500 cells/mm^3 or ≥ 1.5 bil/L; and hemoglobin ≥ 9 g/dL or ≥ 90 g/L). • Adequate hepatic function (aspartate aminotransferase [AST/SGOT] ≤ 3x upper normal limit [UNL], alanine aminotransferase [ALT/SGPT] ≤ 3x UNL (≤ 5x UNL if liver metastases present), bilirubin ≤ 1.5x UNL). • Adequate renal function (serum creatinine ≤ 2.0 mg/dL or 177 $\mu\text{mol/L}$). • Adequate coagulation (“International Normalized Ratio or INR must be ≤ 1.5” unless on therapeutic blood thinners) 	
			12. Is the patient free from evidence of active infection and no serious infection within the past month?	
			13. Is the patient mentally competent, able to understand and willing to sign the informed consent document?	
Yes	No	N/A	Exclusion Criteria (All responses must be NO in order to enter study)	
			1. Is the patient receiving any other standard or investigational treatment for their cancer, or have they received any other investigational agent for any indication within the past 2 weeks prior to initiation of CPI-613 treatment?	
			2. Does the patient have a serious medical illness that would potentially increase his or her risk for toxicity?	
			3. Does the patient have any active uncontrolled bleeding, or a bleeding diathesis (e.g., active peptic ulcer disease)?	
			4. Is the patient a pregnant woman, or a woman of child-bearing potential who is not using reliable means of contraception?	
			5. Is the patient a lactating female?	
			6. Is the patient a fertile man who is unwilling to practice contraceptive methods during the study period?	
			7. Is the patient’s life expectancy less than 3 months?	
			8. Does the patient have any condition or abnormality which may, in the opinion of the investigator, compromise his or her safety?	
			9. Is the patient unwilling or unable to follow protocol requirements?	
			10. Does the patient experience dyspnea with moderate exertion?	
			11. Does the patient have clinically significant pleural or pericardial effusions?	

Comprehensive Cancer Center of Wake Forest University
A Pilot Study: Open-Label Clinical Trial of CPI-613 in Patients with Advanced Bile Duct
Cancers
CCCWFU # 59212

CCCWFU # 59212

Eligibility Checklist

			12. Does the patient have active heart disease including but not limited to symptomatic congestive heart failure, symptomatic coronary artery disease, symptomatic angina pectoris, symptomatic myocardial infarction, or symptomatic congestive heart failure?	
			13. Does the patient have a history of myocardial infarction that is <1 year prior to registration, or previous congestive heart failure (<1 year prior to registration) requiring pharmacologic support or with Left Ventricular Ejection Fraction <50%?	
			14. Does the patient have a history of additional risk factors for torsade de pointes (e.g., heart failure, hypokalemia, family history of Long QT Syndrome)?	
			15. Does the patient have evidence of active infection, or serious infection within the past month?	
			16. Does the patient have known HIV infection?	
			17. Does the patient have baseline troponin levels greater than the institutional limit of normal?	
			18. Will the patient have received cancer immunotherapy of any type within the past 2 weeks prior to initiation of CPI-613 treatment?	
			19. Does the patient require immediate palliative treatment of any kind, including surgery?	
			20. Has the patient received a chemotherapy regimen with stem cell support in the previous 6 months?	
			21. Does the patient have a history of prior illicit drug addiction?	
			22. Does the patient have any condition or abnormality which may, in the opinion of the investigator, compromise his or her safety?	

Signature: _____ Date: _____

Please send source documentation with Eligibility Form.

Comprehensive Cancer Center of Wake Forest University
A Pilot Study: Open-Label Clinical Trial of CPI-613 in Patients with Advanced Bile Duct
Cancers
CCCWFU # 59212

CCCWFU # 59212

Protocol Registration Form

DEMOGRAPHICS

Patient: Last Name: _____ First Name: _____
MRN: _____ DOB (mm/dd/yy): ____/____/____
SEX: _____ Male Ethnicity (choose one): Hispanic
 Female Non-Hispanic
Race (choose all that apply): WHITE BLACK ASIAN
 PAIFIC ISLANDER NATIVE AMERICAN
Height: ____ . ____ inches Weight: ____ . ____ lbs.(actual)
Surface Area: ____ . ____ m²
Zip Code: _____
Primary Diagnosis: _____
Date of Diagnosis: ____ / ____ / ____
Performance Status : _____
Stage of Disease: _____

CURRENT DISEASE STATUS AT REGISTRATION: _____

Prior Therapies/ Protocol # if applicable	Start / End Date of Prior Therapy	Best Response (PROG, TE, STAB, ,NE, CR, PR, NE)	Date of Best Response	Date of Relapse	Duration of Best Response (in Months)
#1 _____	____ / ____	_____	_____	_____	_____
#2 _____	____ / ____	_____	_____	_____	_____
#3 _____	____ / ____	_____	_____	_____	_____
#4 _____	____ / ____	_____	_____	_____	_____

PROTOCOL INFORMATION

Date of Registration: ____ / ____ / ____
MD Name (last) : _____
Date protocol treatment started: ____ / ____ / ____
Informed written consent: YES NO
(consent must be signed prior to registration)
Date Consent Signed: ____ / ____ / ____
PID # (to be assigned by ORIS): _____

Protocol Registrar can be contact by calling [contact] between 8:30 AM and 4:00 PM, Monday – Friday.

Completed Eligibility Checklist and Protocol Registration Form must be hand delivered, faxed or e-mailed to the registrar at [name] or [contact].

Comprehensive Cancer Center of Wake Forest University
A Pilot Study: Open-Label Clinical Trial of CPI-613 in Patients with Advanced Bile Duct
Cancers
CCCWFU # 59212

**CCCWFU # 59212 Eligibility Source Documentation Checklist
(to be submitted with Protocol Registration Form)**

Source Documents Needed		✓ or N/A
1	Pathology report confirming histologically and cytologically proven cholangiocarcinoma of any type	
2	Lab report documenting all initial required lab values	
3	Radiologic documentation that patient has local, locally-advanced, or metastatic disease that has shown progression	
4	Documentation of measurable tumor according to RECIST 1.1 criteria with at least one unidimensionally measurable target lesion	
5	Documentation that the patient is free of evidence of biliary duct obstruction (unless obstruction is controlled by local treatment) OR documentation that patient's biliary tree can be decompressed by endoscopic or percutaneous stenting with subsequent bilirubin to below 1.5x ULN	
6	Documentation that the patient is free from acute toxic effects from previous treatment superior to grade 1	
7	Documentation of ECOG performance status of 0, 1 or 2	
8	Documentation of expected survival > 3 months	
9	Most recent H&P documenting patient is 18 – 80 years of age	
10	For female patients of childbearing potential, documentation that patient agrees to use accepted contraceptive methods during the study and to have a negative serum or urine pregnancy test within 1 week prior to initiation of treatment	
11	For male patients, documentation of infertility OR for fertile men, documentation that patient agrees to practice effective contraceptive methods during the study	
12	Lab report performed (≤ 2 weeks) documenting the following values: 
 • Granulocyte count $\geq 1500/\text{mm}^3$ • White blood cell ≥ 3500 cells/mm^3 or ≥ 3.5 bil/L • Platelet count $\geq 100,000$ cells/mm^3 or ≥ 100 bil/L • Absolute neutrophil count ≥ 1500 cells/mm^3 or ≥ 1.5 bil/L • Hemoglobin ≥ 9 g/dL or ≥ 90 g/L • Aspartate aminotransferase [AST/SGOT] ≤ 3x upper normal limit [UNL] • Alanine aminotransferase [ALT/SGPT] ≤ 3x UNL (≤ 5x UNL if liver metastases present) • Bilirubin ≤ 1.5x UNL • Serum creatinine ≤ 2.0 mg/dL or 177 $\mu\text{mol/L}$ • International Normalized Ratio or INR must be ≤ 1.5 unless on therapeutic blood thinners 	
13	Documentation that the patient is free from evidence of active infection and has had no serious infection within the past month	
14	Documentation that the patient is mentally competent	
15	Copy of signed consent form	
16	Documentation that the patient is not currently receiving any other standard or	

Comprehensive Cancer Center of Wake Forest University
A Pilot Study: Open-Label Clinical Trial of CPI-613 in Patients with Advanced Bile Duct
Cancers
CCCWFU # 59212

Source Documents Needed		✓ or N/A
	investigational treatment for their cancer, and has not received any other investigational agent for any indication within the past 2 weeks prior to initiation of treatment with CPI-613	
17	Documentation that the patient does not have a serious medical illness, condition, or abnormality that would potentially increase his or her risk for toxicity or compromise his or her safety	
18	Documentation that the patient does not have evidence of active uncontrolled bleeding or a bleeding diathesis	
19	Documentation that the patient is not pregnant, lactating, or (if a woman of childbearing potential) using a reliable means of contraception	
20	Documentation that the patient is not unwilling or unable to follow protocol requirements	
21	Documentation that the patient does not experience dyspnea with moderate exertion	
22	Documentation that the patient does not have clinically significant pleural or pericardial effusions	
23	Documentation that the patient does not have active heart disease including but not limited to: symptomatic congestive heart failure, symptomatic coronary artery disease, symptomatic angina pectoris, symptomatic myocardial infarction, or symptomatic congestive heart failure	
24	Documentation that the patient does not have a history of myocardial infarction that is <1 year prior to registration, or previous congestive heart failure (<1 year prior to registration) requiring pharmacologic support or with Left Ventricular Ejection Fraction <50%)	
25	Documentation that the patient does not have a history of additional risk factors for torsade de pointes (e.g., heart failure, hypokalemia, family history of Long QT Syndrome)	
26	Documentation that the patient's albumin is <2.5 g/dL or <25 g/L	
27	Documentation that the patient does not have known HIV infection	
28	Documentation that the patient does not have baseline troponin levels greater than the institutional limit of normal	
29	Documentation that the patient has not received cancer immunotherapy of any type within the past 2 weeks prior to initiation of treatment with CPI-613	
30	Documentation that the patient does not require immediate palliative treatment of any kind, including surgery	
31	Documentation that the patient has not received a chemotherapy regimen with stem cell support in the previous 6 months	
32	Documentation that the patient does not have a history of prior illicit drug addiction	

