3.0 PATIENT ELIGIBILITY CRITERIA

3.1 Inclusion Criteria

Patients must meet all of the following inclusion criteria before enrollment:

- A. Histologically and cytologically proven bile duct cancer of any type (including intrahepatic cholangiocarcinomas, extrahepatic primary cholangiocarcinomas, hilar cholangiocarcinomas, cholangiocarcinomas located in the gall bladder or hepatic capsule effraction, and carcinoma of the Ampulla of Vater, etc.) that is not amenable

Comprehensive Cancer Center of Wake Forest University
A Pilot Study: Open-Label Clinical Trial of CPI-613 in Patients with Advanced Bile Duct
Cancers
CCCWFU # 59212

- to surgery, radiation, or combined modality therapy with curative intent, and has failed or is not eligible for available chemotherapies such as gemcitabine with or without platinum.
- B. Local, locally-advanced, or metastatic disease documented as having shown progression on a scan (e.g., CT, MRI).
 - C. Measurable tumor according to RECIST 1.1 criteria with at least one unidimensionally measurable target lesion.
 - D. No evidence of biliary duct obstruction, unless obstruction is controlled by local treatment or, in whom the biliary tree can be decompressed by endoscopic or percutaneous stenting with subsequent reduction in bilirubin to below 1.5x Upper Level of Normal (ULN).
 - E. No acute toxic effects from previous treatment superior to grade 1 at the start of the study.
 - F. Eastern Cooperative Oncology Group (ECOG) performance status being 0-2.
 - G. Expected survival >3 months.
 - H. Male and female patients 18 years of age and older.
 - I. Women of child-bearing potential (i.e., women who are pre-menopausal or not surgically sterile) must use accepted contraceptive methods (abstinence, intrauterine device [IUD], oral contraceptive or double barrier device) during the study, and must have a negative serum or urine pregnancy test within 1 week prior to treatment initiation.
 - J. Fertile men must practice effective contraceptive methods during the study, unless documentation of infertility exists.
 - K. Laboratory values ≤ 2 weeks must be:
 - Adequate hematologic (granulocyte count $\geq 1500/\text{mm}^3$; white blood cell [WBC] ≥ 3500 cells/ mm^3 or ≥ 3.5 bil/L; platelet count $\geq 100,000$ cells/ mm^3 or ≥ 100 bil/L; absolute neutrophil count [ANC] ≥ 1500 cells/ mm^3 or ≥ 1.5 bil/L; and hemoglobin ≥ 9 g/dL or ≥ 90 g/L).

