4.0 REGISTRATION PROCEDURES

All patients entered on any CCCWFU trial, whether treatment, companion, or cancer control

Comprehensive Cancer Center of Wake Forest University
A Pilot Study: Open-Label Clinical Trial of CPI-613 in Patients with Advanced Bile Duct
Cancers
CCCWFU # 59212

trial, **must** be registered with the CCCWFU Protocol Registrar or entered into the Oncology Research Information System (ORIS) Screening Log within 24 hours of informed consent.

Patients **must** be registered prior to the initiation of treatment.

In order to ensure prompt registration of your patient, please:

1. Complete the Eligibility Checklist (Appendix A)
2. Complete the Protocol Registration Form (Appendix A)
3. Alert the WFUHS registrar by phone, *and then* send the signed Informed Consent Form, Eligibility Checklist and Protocol Registration Form to the registrar, either by fax or e-mail.

Contact Information:

Protocol Registrar [contact]

Protocol Registrar [contact]

Protocol Registrar E-MAIL ([contact])

*Protocol Registration is open from 8:30 AM - 4:00 PM, Monday-Friday.

4. Please fax/e-mail ALL eligibility source documents with registration. Patients **will not** be registered without all required supporting documents.

Note: If labs were performed at an outside institution, please provide a printout of the results. Please ensure that the most recent lab values are sent.

To complete the registration process, the Registrar will:

- assign a patient study number
- register the patient on the study

Comprehensive Cancer Center of Wake Forest University
A Pilot Study: Open-Label Clinical Trial of CPI-613 in Patients with Advanced Bile Duct Cancers
CCCWFU # 59212

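### Three items of the source-document checklist submitted at registration (age, contraception, albumin) do not match Section 3 or the Yes/No Eligibility Checklist

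*Combined protocol and SAP*

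**What the plan says.** Eligibility appears in three places: Sections 3.1 and 3.2, the Yes/No Eligibility Checklist in Appendix A, and the Eligibility Source Documentation Checklist, also in Appendix A. By its own heading, the last accompanies the Protocol Registration Form. Section 4.0 and the opening of Appendix A ask for all eligibility source documents at registration and say that patients will not "be registered without all required supporting documents". Registration must come before treatment.

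The source checklist contains these three items:

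- Item 9 (age): "Most recent H&P documenting patient is 18" to 80; the full range reads "documenting patient is 18 – 80 years of age". Inclusion H in Section 3.1 reads "Male and female patients 18 years of age and older", and inclusion item 8 of the Yes/No checklist asks "Is the patient a male or female age 18 years and older".
- Item 19 (pregnancy, lactation, contraception): "Documentation that the patient is not pregnant, lactating, or (if a woman of childbearing potential) using a reliable means of contraception".
- Item 26 (albumin): documentation that the patient's "albumin is <2.5 g/dL or <25 g/L".

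**The concern.** A registration form should document the protocol's criteria. It should not add to them or reverse them. If the source checklist is applied as written, it describes a different population from Section 3: it has an upper age limit, an albumin requirement that excludes anyone at or above 2.5 g/dL, and a contraception condition pointing the wrong way.

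Two things are at stake. The first is who can enter: a patient who meets every Section 3 criterion could be turned away on paperwork. The second is whether eligibility can be audited. A registrar who sets item 26 aside departs from a listed document, and one who enforces it applies a rule that the protocol does not contain. The contraception item also bears on safety, because exclusion D rests on the drug's unknown teratogenic potential.

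**Working it through.** No sample size, error rate or event count is involved, so there is nothing numerical to reproduce. The check is to compare the three sources item by item.

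| Topic | Sections 3.1 and 3.2 | Yes/No Eligibility Checklist | Source checklist |
|---|---|---|---|
| Age | Inclusion H: 18 and over, no upper limit | Inclusion item 8: same as H | Item 9: 18 to 80 |
| Contraception, women of childbearing potential | Inclusion I: must use it; exclusion D: excluded if not using it | Inclusion item 9 and exclusion item 4: same as Section 3 | Item 10: must agree to use it; item 19, literally: must not be using it |
| Albumin | No criterion | No item | Item 26: below 2.5 g/dL (25 g/L) |

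**Age.** Item 9 is narrower than inclusion H. Anyone over 80 who meets Section 3 fails the item, and nobody outside Section 3 is let in by it.

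**Contraception.** In item 19 a single negation governs three parts: pregnant, lactating, and using contraception. It works for the first two and reverses the third. A woman of childbearing potential who uses contraception satisfies inclusion I and item 10 but fails item 19 as worded.

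**Albumin.** Inclusion K limits blood counts, AST, ALT, bilirubin, creatinine and INR, but not albumin. Section 3.2 does not mention it either. Elsewhere albumin appears only in the list of chemistry analytes in Section 5.2.2. Because chemistry is drawn at screening (Table 5-1), every patient should have a value, so item 26 applies to all. A patient with albumin of 2.5 g/dL or more can meet all of Section 3 and still fail it. Items 25 and 27, on either side, are written as negated exclusions (the patient does not have the condition). Item 26 may therefore be an exclusion that lost its negation, but the documents do not say so. Restoring a negation would also leave an albumin exclusion that Section 3 does not contain.

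**Count.** Three of the 32 numbered items (9, 19 and 26) fail to match, which is 3/32, or about 9% of the form. That measures the form, not the patients. The documents give no distribution of age or albumin and no number of women of childbearing potential, so the proportion of candidates affected cannot be estimated.

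**The case against.** The best defence is that another form decides entry. The Yes/No checklist states its own rule (every inclusion answer yes, every exclusion answer no), and it agrees with Section 3 on age and contraception and has no albumin item. The numbered steps in Section 4.0 name that checklist and the Registration Form, but not the source checklist. The refusal sentence concerns missing documents, and the source checklist offers a tick or a not-applicable mark with no stated pass/fail rule. Item 19 can be read as loose grammar, and item 10 on the same page has the right sense.

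Much of this stands, and it lowers the practical risk. It does not remove the mismatch. The source checklist is the only place that itemises the required source documents, and it is part of the registration packet. Age and albumin apply to every patient, so not-applicable is no natural way out. Nothing in the documents says which Appendix A form prevails.

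Three stronger readings are tempting, and the documents do not support them:

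- A reader might infer that only patients with albumin below 2.5 g/dL could be registered. That assumes staff would apply one line over Section 3 and the Yes/No checklist, and the documents do not show this.
- A reader might infer that item 26 contradicts an albumin threshold in Section 3. Section 3 has none; the item is an extra requirement without a source.
- A reader might infer that, with 10 patients analysed, each patient wrongly refused or admitted shifts a tenth of the analysis set. A refused patient is never in that set, and Cohort 5 still enrols 10. Items 9 and 26 only restrict, so they admit nobody whom Section 3 excludes. Item 19 could do so only if item 10 and both Yes/No contraception items were ignored.

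**Conclusion.** The inconsistency is real and lies in the current text. Item 26 has no counterpart in the eligibility criteria, item 9 adds an upper age limit that Section 3 lacks, and item 19 as worded reverses the contraception requirement. A patient who meets Section 3 could fail the form on any of the three. It should be corrected, but it is a fault in a registration form and not a flaw in the design or analysis.

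The conclusion assumes that the Section 4.0 requirement for supporting documents refers to this checklist, which its heading and content suggest, and that item 19 is read literally. How many patients would be affected, and whether staff worked around the form, cannot be determined. Which albumin or age rule was intended is also not stated, and no view is taken on it here.

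**What to change.** Reconcile items 9, 19 and 26 with Section 3 and the Yes/No Eligibility Checklist:

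- **Items 9 and 26.** The sponsor and investigator should state whether an upper age limit or an albumin limit is intended. If so, put it in Section 3 and in both forms in identical words, with its direction explicit. If not, remove it from the source checklist.
- **Item 19.** Split the contraception clause from pregnancy and lactation, and word it to agree with exclusion D and item 10.

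A sentence saying that Section 3 governs if a form differs would prevent the same problem with later edits. If no new limit is intended, the cost is a corrected form and a minor amendment. If one is, Section 3 and the Yes/No checklist need a short matching change. The sample size and the planned analyses are unaffected.
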